## Hypothesis

In critically ill patients, a post-resuscitation fluid strategy comprising conservative fluid administration and active deresuscitation reduces net fluid balance, is safe and improves outcomes.

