## Objectives

1. To determine the feasibility, safety and clinical outcomes of conservative fluid administration and deresuscitation compared with usual care in critically ill patients
2. To explore biological effects of conservative fluid administration and deresuscitation.

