### Statistical analysis principles

The study will be analysed on an intention to treat basis. Multiple imputation will be used to deal with missing data. A p value of 0.05 will be considered as significant. A single final analysis is planned at the end of the trial.

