## Outcome measures and analysis

The primary endpoint is the fluid balance (mL) during the 24-hour period up to the beginning of study day 3 [continuous variable, measured using a Student's t-test for independent samples].

Secondary Outcomes		
Feasibility outcomes		
Cumulative fluid balance (mL) from ICU admission until the beginning of study days 3 and day 5, and at ICU discharge	Continuous variables	Independent samples t-test (or non-parametric equivalent)
Rates of recruitment as a proportion of patients screened and as a proportion of all patients admitted to ICU (per site)		Descriptive only
Incidence of significant protocol violations (total number of patients, per site, and by nature of protocol violation)		Descriptive only
Safety outcomes		
Incidence of serious adverse events (SAEs) (number of patients with SAEs as a proportion of total)		Chi-squared test / Fisher's exact test
Incidence of adverse events (AEs) (number of patients with AEs as a proportion of total)		Chi-squared test / Fisher's exact test
Efficacy outcomes		
Change in SOFA scores from baseline to the beginning of day 3 and beginning of day 5, overall and individual organ sub scores	Continuous variable	Multiple regression analysis (with baseline scores as covariate)
Mortality (28-day and 180 day)	Discrete variable	Chi-squared test; Kaplan-Meier survival curves; log-rank test +/- Cox proportional hazards model if assumptions met
Duration of mechanical ventilation in survivors and non-survivors	Continuous variable	Independent samples t-test (or non-parametric equivalent); Kaplan-Meier survival curves; log-rank test; +/- Cox proportional hazards model if assumptions met
Length of ICU stay	Continuous variable	Independent samples t-test (or non-parametric equivalent); Kaplan-Meier survival curves; log-rank test; +/- Cox

		proportional hazards model if assumptions met
Incidence of new acute kidney injury defined as KDIGO Stage 3 (before and after correction for fluid balance) up to the beginning of day 5	Discrete variable	Chi-squared test
Cognitive dysfunction at 180 days	Discrete variable	Chi-squared test
Health-related quality of life (HR-QoL) at 180 days	Ordinal variable	Mann-Whitney test
Incidence of anxiety and depression	Discrete variable	Chi-squared test
Incidence of Post-traumatic stress disorder	Discrete variable	Chi-squared test
Exploratory outcomes		

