## Dummy Tables and Diagrams

The following are indicative of the approach used to present data, rather than the precise format.

Figure 1. Study flow diagram.

[figure not shown]

Table 1. Patient characteristics at randomisation.

Variables	Control	Intervention
Age	Mean (SD)	Mean (SD)
Gender:		
Male	N (%)	N (%)
Female	N (%)	N (%)
Type of admission:		
Emergency	N (%)	N (%)
Elective	N (%)	N (%)
Operative status:		
Surgical	N (%)	N (%)
Non-surgical	N (%)	N (%)
Primary organ system involvement:		
Respiratory	N (%)	N (%)
Cardiovascular	N (%)	N (%)
Neurological	N (%)	N (%)
Renal	N (%)	N (%)
Gastrointestinal	N (%)	N (%)
Other	N (%)	N (%)
Subgroups:		
Acute Respiratory Distress Syndrome	N (%)	N (%)
Sepsis	N (%)	N (%)
Traumatic Brain Injury	N (%)	N (%)
Hyperinflammatory phenotype	N (%)	N (%)
APACHE II score	Mean (SD)	Mean (SD)
Baseline SOFA score	Mean (SD)	Mean (SD)
KDIGO stage:		
1	N (%)	N (%)
2	N (%)	N (%)
3	N (%)	N (%)
Vasopressor use	N (%)	N (%)
Serum lactate	Mean (SD)	Mean (SD)
Renal Replacement Therapy use	N (%)	N (%)
Oxygenation index	Mean (SD)	Mean (SD)
Oedema in > 1 peripheral site	N (%)	N (%)
Cumulative fluid balance	Mean (SD)	Mean (SD)

Table 2. Key outcomes

	Control	Intervention	P value
Primary outcome			
Fluid balance over 24 hours up to Day 3 (mL)	Mean (SD)	Mean (SD)	x.xxx
Feasibility outcomes			
Cumulative fluid balance from ICU admission up to Day 3	Mean (SD)	Mean (SD)	x.xxx
Cumulative fluid balance from ICU admission up to Day 5	Mean (SD)	Mean (SD)	x.xxx
Clinical outcomes			
Mortality at 28 days:			
Total	N (%)	N (%)	x.xxx
Acute Respiratory Distress Syndrome	N (%)	N (%)	
Sepsis	N (%)	N (%)	
Traumatic Brain Injury	N (%)	N (%)	
Hyperinflammatory phenotype	N (%)	N (%)	
Duration of mechanical ventilation in survivors	Median (IQR) # , N=x	Median (IQR) # , N=x	x.xxx
Length of ICU stay in survivors	Median (IQR) # , N=x	Median (IQR) # , N=x	x.xxx
Change in SOFA scores baseline to day 3	Mean (SD)	Mean (SD)	x.xxx
Change in SOFA scores baseline to day 5	Mean (SD)	Mean (SD)	x.xxx
Incidence of new AKI (KDIGO Stage 3)	N (%)	N (%)	x.xxx
Before correction for fluid balance			
After correction for fluid balance			

\*Individual SOFA organ function scores to be reported in an appendix. #Mean (SD) to be reported if normally distributed

Table 3. Process measures

Recruitment rates (% of screened patients / % of admitted patients)*:			
Total	xx.x% / yy.y%		N/A

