Number of protocol violations* (% of included patients):			
Total	N (%)	N (%)	N/A
Eligibility	N (%)	N (%)	
Study conduct	N (%)	N (%)	
Other	N (%)	N (%)	
Incidence of adverse events:			
Number of patients experiencing AEs	N (%)	N (%)	x.xxx
Protocol specified expected AEs	N (%)	N (%)	x.xxx
Total of AEs #	N (%)	N (%)	x.xxx
AE 1 #	N (%)	N (%)	x.xxx

AE 2 #	N (%)	N (%)	x.xxx
AE 3 #	N (%)	N (%)	x.xxx
Other	N (%)	N (%)	x.xx
Incidence of serious adverse events (% of included patients)	N (%)	N (%)	x.xxx

\*Data to be reported by site in appendix. #3 most frequent reported individually. Full list in appendix to main manuscript. Full list of AR, SARs, and SUSARs in appendix (if any).

Long term (180-day) outcomes, and exploratory outcomes, will be reported in a separate manuscript.

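### Safety is to be compared by a chi-squared or Fisher p-value alone; the plan should pre-specify a risk difference with a 95% confidence interval, because a non-significant test at 90 per arm cannot rule out important harm

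*SAP*

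**What the plan says.** Safety appears in the SAP's Hypothesis, which states that the strategy "reduces net fluid balance, is safe and improves outcomes", and in its first Objective: "To determine the feasibility, safety and clinical outcomes of conservative fluid administration and deresuscitation compared with usual care in critically ill patients".

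Under Outcome measures and analysis, the two outcomes classed as safety outcomes are the proportions of patients with SAEs and with AEs. The method given for each is "Chi-squared test / Fisher's exact test". No effect measure or interval is attached to either. Statistical analysis principles adds one general criterion: "A p value of 0.05 will be considered as significant".

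In Dummy Tables and Diagrams, the row "Incidence of serious adverse events (% of included patients)" of Table 3 has a number and percentage for each arm and a p-value. The AE rows have the same layout. Table 2 likewise has arm summaries and a p-value. The section introduces these tables with a caveat: "The following are indicative of the approach used to present data, rather than the precise format".

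The only confidence intervals in the SAP are in the Background, for a cited meta-analysis.

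**The concern.** A test of no difference can show harm when harm is large enough. It cannot show safety, because failing to reject is also what a small trial produces when the harm is real but moderate. This trial's size was set by a 750 mL difference in fluid balance, and nothing in that calculation concerns event rates.

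The question that follows from the safety hypothesis is how large an excess of SAEs the data still allow. An interval for the between-arm difference answers it; a p-value does not. If the analysis is run as listed, the safety result could be two percentages and a non-significant p-value, with the upper end of the plausible excess left unstated. A pilot that should inform a larger trial needs that figure.

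**Working it through.** **Inputs from the SAP.** Difference 750 mL, SD 1512 mL, two-sided 0.05, 90% power, 3% drop-out, 90 per arm (Sample Size Calculation); 1:1 allocation (Randomisation). **Assumed:** control SAE rates of 5% to 30%, since the SAP gives no rate.

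**1. The plan's own figure.** Normal approximation: n per arm = 2(1.96 + 1.2816)² × (1512/750)² = 2 × 10.51 × 4.064 = 85.4, so 86. The t-based calculation gives 86.4, so 87 per arm, with power 0.902. Allowing for drop-out, 174/0.97 = 179.4, so 180. The stated 174 and 180 reproduce. They concern fluid balance only.

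**2. Precision for SAEs at 90 per arm.** With equal rates p in both arms, the 95% half-width of the risk difference is 1.96 × √(2p(1−p)/90). At p = 10% this is 1.96 × √(0.18/90) = 0.088.

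- 5%: 6.4 points
- 10%: 8.8 points
- 20%: 11.7 points
- 30%: 13.4 points

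**3. Power of the planned test.** For each pair of true rates, the two binomial probabilities were multiplied and summed over all tables for which the uncorrected chi-squared test gives p < 0.05.

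- Doubling: 24% (5% v 10%), 47% (10% v 20%), 51% (11% v 22%), 68% (15% v 30%), 84% (20% v 40%), 98% (30% v 60%)
- 1.5-fold increase: 17% (10% v 15%), 34% (20% v 30%)

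Fisher's test is more conservative, so these figures are the favourable case. Drop-out changes little: for 10% v 20%, the normal approximation gives 0.467 at 90 per arm and 0.455 at 87.

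**4. A worked result: 16/90 (17.8%) against 9/90 (10.0%).**

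- Pooled rate 25/180 = 0.139; standard error √(2 × 0.139 × 0.861/90) = 0.0516; z = 0.0778/0.0516 = 1.51; p = 0.13. Fisher p = 0.20.
- Risk difference 0.178 − 0.100 = +7.8 points; Newcombe 95% interval −2.5 to +18.1. Risk ratio 16/9 = 1.78.

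An observed exact doubling, 18/90 against 9/90, gives p = 0.060 (chi-squared) or 0.094 (Fisher), with a difference of +10 points and an interval of −0.5 to +20.5.

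Both results are non-significant, yet they leave excesses of about 18 and 20 points compatible with the data.

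**The case against.** The strongest reply has five parts.

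- **The SAP never says that a non-significant test will be reported as safety.** This stands. A reader might infer that rule from the hypothesis, the 0.05 criterion and the lack of an estimate, but the text does not state it. The point is what the plan omits.
- **A doubling would not generally be missed.** This also stands. A reader might conclude that a doubling would more often than not give p > 0.05, but that holds only at control rates of about 10% or below. Power is already 51% at 11% and reaches 84% at 20%. A 1.5-fold increase is poorly detected at both 10% and 20%.
- **Safety information is not confined to p-values.** Table 3 has counts by arm for AEs and SAEs, and full event lists are planned for an appendix. A reader could derive the difference and its interval from the counts. So the data are not lost, but the estimate and its precision are not pre-specified.
- **The tables are only indicative.** That leaves room for an interval without committing to one, and the methods listed for the safety outcomes have the same gap.
- **Other outcomes do get estimates.** Secondary analyses plans a regression with treatment as the main exposure, SOFA change is to be analysed by regression, and mortality may have a Cox model. It would therefore be wrong to say that the whole plan lacks effect sizes. The Cox model is not assigned to SAEs or AEs, and no difference or interval is named alongside the primary t-test.

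The unseen protocol does not answer the point, since the choice of effect measure and interval belongs in an SAP.

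**Conclusion.** The point holds as an inexpensive improvement to the analysis. The SAP hypothesises safety but names only a significance test for SAEs and AEs, in a trial sized for another outcome. A non-significant result at 90 per arm would leave an important excess of harm open; in the worked example the upper limit is 18.1 points.

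The power figures rest on assumed control SAE rates. They show weak detection of a doubling at 5% to 10%, fair detection at 15%, and good detection at 20% or more. The general point, that non-significance is not evidence of safety and that precision should be reported, does not depend on the rate chosen.

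The documents do not support the stronger claims that the plan will equate p > 0.05 with safety, or that no outcome will have an effect estimate.

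**What to change.** In the safety rows of Outcome measures and analysis:

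- Make the risk difference (with the risk ratio) and its 95% confidence interval the main analysis, for patients with at least one SAE and for patients with at least one AE. Name the interval method, for example Newcombe.
- Keep the chi-squared or Fisher test as secondary.
- State that p > 0.05 is not evidence of safety, and that the interval will be reported as the range of harm compatible with the data.

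A rule that judges safety on the upper confidence limit would need a threshold. The SAP has none, so reporting the interval is the appropriate commitment here.

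In Dummy Tables and Diagrams, add a column for the difference (95% CI) to Table 2 and Table 3. For the primary outcome this is the mean difference belonging to the planned t-test.

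The cost is a few lines of SAP text and one table column, with no new data. The one small downside is that the safety conclusion will be more cautious.

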## Secondary analyses

Secondary multiple regression analysis will be performed with treatment allocation as the main exposure. The following key covariates will be forced into the model: age, APACHE II score, presence of ARDS, vasopressor use at baseline. Additional covariates for inclusion in the model will be selected based on clinical plausibility.

We will undertake a secondary per-protocol analysis. This information will be valuable in differentiation between treatment failure (the treatment did not have the intended effect) and process failure (intervention not delivered as intended).

If there is evidence of a difference in the outcome of cognitive dysfunction between treatment groups, we will use path analysis to attempt to ascertain whether the effect of treatment group assignment on cognitive function is mediated by cerebral oxygenation.

For the exploratory outcomes, we will undertake secondary analyses using multivariate regression analysis with fluid balance as the main exposure and treatment group assignment as a covariate.

At a later stage, we will investigate the relationship between cerebral and tissue oxygenation and cardio-respiratory physiological variables such as heart rate, mean arterial pressure, and arterial oxygen saturation.

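### New stage 3 kidney injury is compared without its baseline KDIGO stage; the test is valid, but stratifying by that stage is a cheap gain in precision

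*SAP*

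**What the plan says.** Under Outcome measures and analysis, the efficacy row reads "Incidence of new acute kidney injury defined as KDIGO Stage 3 (before and after correction for fluid balance) up to the beginning of day 5", and its analysis is a "Chi-squared test" with no covariate. In the same table, change in SOFA score is analysed by "Multiple regression analysis (with baseline scores as covariate").

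Under Dummy Tables and Diagrams, Table 1 tabulates KDIGO stages 1, 2 and 3 at randomisation. Table 2 shows counts, percentages and a p value for new AKI, with one line before and one after correction for fluid balance, and no effect estimate. The SAP says of these tables: "The following are indicative of the approach used to present data, rather than the precise format".

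Under Secondary analyses: "Secondary multiple regression analysis will be performed with treatment allocation as the main exposure". The outcomes of that regression are not named. Its fixed covariates are given: "The following key covariates will be forced into the model: age, APACHE II score, presence of ARDS, vasopressor use at baseline". Then: "Additional covariates for inclusion in the model will be selected based on clinical plausibility".

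Under Randomisation, site is the only stratification factor and allocation is 1:1.

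**The concern.** The intervention limits fluid and removes it with diuretics or renal replacement therapy, so kidney injury is a plausible harm, and safety is among the stated objectives. The trial is sized for fluid balance, so stage 3 events may be few.

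A patient who enters at stage 2 is closer to stage 3 than one who enters at stage 0. If the arms differ by chance in baseline stage, that difference passes straight into the unadjusted comparison. The design does not balance baseline stage, and the AKI row does not use it.

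The correction for fluid balance does not fill this gap. It yields two versions of the outcome and is not an adjustment for baseline renal status.

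**Working it through.** **The plan's own figures.** The SAP gives no event rate, effect or power for AKI. Its only sample size is for fluid balance, and that reproduces: a two-sided t-test at 5% with 90% power, difference 750 mL and SD 1512 mL needs 86.4, so 87 per group or 174. Then 174 / 0.97 = 179.4, so 180. The 90 per arm is used below.

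**Assumptions (none is in the SAP).**
- 90 per arm, none at stage 3 at baseline.
- Baseline stage 0/1/2 in proportions 60/20/20, 75/15/10 or 40/30/30%.
- Control risk of new stage 3 of 6, 9, 12 or 20%.
- Odds of stage 3 multiplied by 1, 2.2, 4 or 8 per baseline stage.
- Treatment odds ratio 1 (null) or 2.
- Both tests two-sided at 5% without continuity correction. The SAP does not say whether its chi-squared test is corrected; assuming it is not favours the plan.

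**Tests compared.** Crude chi-squared, and Cochran-Mantel-Haenszel (CMH) over baseline stages s:

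CMH = [Σ(a_s − n1_s·m_s/N_s)]² / Σ[n1_s·n0_s·m_s·(N_s − m_s) / (N_s²(N_s − 1))]

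Here a_s is events in the intervention arm, n1_s and n0_s are the arm sizes, m_s is total events and N_s is total patients in stage s. Each setting had 40,000 simulated trials, with a standard error of at most 0.25 points on the overall rates.

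**Step 1: validity.** With no treatment effect, chi-squared rejects in 4.2 to 5.2% of trials and CMH in 4.7 to 5.1%. Both are valid.

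**Step 2: power.** Mix 60/20/20, control risk 12%, treatment odds ratio 2:

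| Odds ratio per baseline stage | Chi-squared | CMH | Gain (points) |
|---|---|---|---|
| 1 | 39.7% | 39.6% | −0.1 |
| 2.2 | 34.8% | 36.7% | +1.9 |
| 4 | 26.8% | 31.6% | +4.8 |
| 8 | 18.9% | 25.9% | +7.0 |

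Over all mixes and control risks the gain is −0.5 to 0 points at 1, 0 to 2.7 at 2.2, 1.1 to 7.7 at 4, and 1.8 to 10.6 at 8. An odds ratio of 8 per stage means 8 × 8 = 64 between stage 2 and stage 0, so that row is an extreme case and not an expectation.

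As a cross-check, risks were set directly at 5/12/30% for stages 0/1/2 (mix 60/25/15). Power at treatment odds ratios 0.5, 2 and 2.5 was 21, 30 and 50% for chi-squared against 21, 33 and 54% for CMH.

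**Step 3: chance imbalance.** Take the 60/20/20 mix, 12% control risk and odds ratio 4 per stage. The stage risks are then 3.5, 12.7 and 36.8%, and 0.6 × 0.0351 + 0.2 × 0.127 + 0.2 × 0.3678 = 0.120. Move 10 points from stage 0 to stage 2 in one arm, with no treatment effect: 0.5 × 0.0351 + 0.2 × 0.127 + 0.3 × 0.3678 = 0.153. The crude odds ratio becomes (0.153/0.847) / (0.120/0.880) = 1.32 to 1.33, although the true value is 1. Over the 60/20/20 and 75/15/10 mixes it is 1.18 to 1.23 at odds ratio 2.2 per stage and 1.32 to 1.47 at 4.

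A gap of 10 points or more in the share at stage 2 arises in about 11% of trials under the 60/20/20 mix, and in 3 to 17% across mixes. In those trials, at 12% control risk, mix 60/20/20 and no treatment effect, chi-squared rejects in about 7% at odds ratio 2.2 per stage and about 10% at 4. CMH stays near 5%.

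**Step 4: denominator.** If 5 to 20% of patients are at stage 3 at baseline, counting them as non-events instead of excluding them costs 0.2 to 1.0 points of power.

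**The case against.** The strongest reply is that there is no defect. An unadjusted comparison is valid in a randomised trial, and this is one secondary outcome of a pilot. That stands.

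A reader might infer from the SOFA row that the plan is inconsistent. It is not. Baseline adjustment of a continuous change score is standard and sets no rule for binary outcomes; the other binary rows name no covariate, and the primary t-test is also unadjusted. Simple comparisons first and a regression second is a coherent plan.

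A reader might also infer that baseline renal status is ignored. The documents do not support that either: the secondary regression could cover AKI, and baseline stage could enter it on clinical plausibility. What remains is that the outcomes are unnamed and this covariate is not fixed before the data are seen.

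Third, the rejection rates in Step 3 concern only trials picked for their imbalance. They must not be read as the trial's false-positive rate, which is nominal. The shifts in the odds ratio are also small beside the sampling error. At 90 per arm and 12% risk the SE of the log odds ratio is √[2 × (1/10.8 + 1/79.2)] = 0.46, so a 95% interval around 1 runs from about 0.41 to 2.46. Readers could see an imbalance in Table 1, though seeing it does not correct the estimate.

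Finally, the size of the gain depends wholly on assumed rates. That also stands.

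**Conclusion.** The point holds as an optional improvement. The SAP makes no error and contradicts nothing here; it leaves a baseline value that will already be held out of the one comparison where it is most likely to matter. Under the assumed rates, stratifying adds about 0 to 3 points of power if baseline stage is weakly prognostic (odds ratio 2.2 per stage or less) and about 1 to 8 points at 4 per stage. It also keeps the error rate near 5% when baseline stage happens to be unbalanced.

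Power stays low with either test, so an odds ratio with its interval would tell a reader more about renal harm than a p value. That baseline stage is prognostic is likely on clinical grounds but is not documented in the SAP.

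**What to change.** In the AKI row of Outcome measures and analysis, specify: among patients not at KDIGO stage 3 at baseline, compare new stage 3 AKI by the Cochran-Mantel-Haenszel test stratified by baseline KDIGO stage (0, 1, 2). Report N (%) per arm and the Mantel-Haenszel odds ratio with 95% CI, for the outcome before and after correction for fluid balance. Say that the strata are the baseline stages as tabulated in Table 1 for both versions of the outcome. The crude chi-squared comparison may be kept alongside. The restriction also settles how patients already at stage 3 count, which the SAP does not state, though the protocol may.

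The cost is a change of SAP wording and an estimate column for this row of Table 2. Stage 3 remains the endpoint, and the stratifier is already listed in Table 1. There are two downsides: up to 0.5 points of power are lost if baseline stage is not prognostic, and the stratified odds ratio is conditional on stage, so it will differ from the crude one and should be labelled as such.

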### Randomisation

Patients will be randomised a minimum of 24 hours and a maximum of 48 hours following ICU admission. Randomisation will be stratified by study site. Subjects will be randomised in a 1:1 ratio using blocks of variable size.

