Plasma levels of markers of endothelial injury (Angiopoietin I/II and Ang-1/2, Syndecan-1, total protein, plasma albumin, and protein permeability (albumin: $\alpha$ 2-macroglobulin ratio)), absolute levels and change from baseline	Continuous variables	Independent samples t-test (or non-parametric equivalent); Repeated measures ANOVA if applicable. Scatterplots and Pearson's correlation coefficient or non-parametric alternative if applicable.
Plasma levels of Inflammatory mediators e.g. CRP, TNF $\alpha$ , IL6, IL8: absolute levels and change from baseline	Continuous variables	Independent samples t-test (or non-parametric equivalent); Repeated measures ANOVA if applicable. Scatterplots and Pearson's correlation coefficient or non-parametric alternative if applicable.
Cardiac function (echocardiographic measures including left ventricular ejection fraction, E/E' ratio)	Continuous variables	Independent samples t-test (or non-parametric equivalent)
Renal function and injury (plasma and urine levels of Cystatin C and NGAL), absolute levels and change from baseline	Continuous variables	Independent samples t-test (or non-parametric equivalent); Repeated measures ANOVA if applicable. Scatterplots and Pearson's correlation coefficient or non-parametric alternative if applicable.
Cerebral oximetry (NIRS measurement of regional cerebral oxygen saturation), mean and minimum rScO 2 level, proportion of time spent with rScO 2 below thresholds of 50%, 65%, and 75%	Continuous variables	Independent samples t-test (or non-parametric equivalent)
Tissue oxygenation (NIRS measurement of muscle tissue oxygen saturation), mean and minimum rScO 2 level	Continuous variables	Independent samples t-test (or non-parametric equivalent)

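### The endothelial, inflammatory and renal markers have no baseline-adjusted comparison between arms and no main form; one ANCOVA per marker would be a minor, nearly free improvement.

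*SAP*

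**What the plan says.** In the SAP's Outcome measures and analysis table, three exploratory rows (endothelial injury, inflammatory mediators, renal function and injury) define each marker as "absolute levels and change from baseline". The method column for all three reads "Independent samples t-test (or non-parametric equivalent); Repeated measures ANOVA if applicable", followed by scatterplots and correlation. No baseline covariate appears, and neither form is marked as the one that answers the question.

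In the same table, under efficacy outcomes, change in SOFA is analysed by "Multiple regression analysis (with baseline scores as covariate").

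Two regressions under Secondary analyses could bear on the markers:

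- The allocation model. Its required covariates are stated: "The following key covariates will be forced into the model: age, APACHE II score, presence of ARDS, vasopressor use at baseline". It then adds: "Additional covariates for inclusion in the model will be selected based on clinical plausibility". A baseline marker value may enter but need not.
- The model written for the exploratory outcomes, a "multivariate regression analysis with fluid balance as the main exposure and treatment group assignment as a covariate". Its main exposure is fluid balance rather than arm, and it names no baseline marker value.

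The echocardiography and NIRS rows list no change from baseline and are outside this point.

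**The concern.** A follow-up level compared without its baseline value carries variation between patients that the baseline could remove. A change score removes that variation with a fixed slope of one, whatever the true slope is. ANCOVA estimates the slope. The SAP adopts this approach for SOFA but not for the markers, and gives no reason.

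Two things are at stake, both confined to Objective 2 (biological effects). The first is precision, which can be recovered from baseline samples that a change score needs anyway. The second is that level and change can give different verdicts on the same marker. With no main form named, the choice of which to stress can follow the result.

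**Working it through.** **The plan's own figure.** The SAP gives no calculation for the markers. Its one calculation, the primary sample size, reproduces: 2 × (1.960 + 1.282)² × (1512/750)² = 85.4, so 86 per arm by the normal approximation. Exact t-test power is 90.2% at the stated 87 per arm, and 174/0.97 = 179.4, so 180. Nothing below depends on an error there.

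**Inputs.** From the SAP: 1:1 allocation and a 0.05 level. Assumed, because the SAP gives neither: the correlation r between baseline and follow-up (range 0.3, 0.5, 0.7), and the ratio s of baseline SD to follow-up SD.

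**Variance of the arm difference**, with the level test set to 1:

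- level: 1
- change: 1 + s² − 2rs
- ANCOVA: 1 − r²

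Since 1 + s² − 2rs = (1 − r²) + (s − r)², ANCOVA never has the larger variance. It equals level only at r = 0 and change only at s = r. The cost is one degree of freedom.

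**Equal variances (s = 1).** Relative to ANCOVA, the variance is 2/(1 + r) for change and 1/(1 − r²) for level. The effect is set so that ANCOVA has 80% power (noncentrality 1.96 + 0.84 = 2.80). Each other test has noncentrality 2.80 divided by the square root of its ratio. At r = 0.5, for example, 2.80/√1.333 = 2.43, which gives 68% power.

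| r | Change: ratio | Change: power | Level: ratio | Level: power |
|---|---|---|---|---|
| 0.3 | 1.54 | 62% | 1.10 | 76% |
| 0.5 | 1.33 | 68% | 1.33 | 68% |
| 0.7 | 1.18 | 73% | 1.96 | 52% |

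To match ANCOVA at 180 patients, the change test would need 180 × ratio = 277/240/212 patients and the level test 198/240/353. The ratios, and so the powers, do not depend on whether 180 or 174 is used.

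**Disagreement.** The level and change statistics have correlation √((1 − r)/2) = 0.59/0.50/0.39. From the bivariate normal with the noncentralities above, exactly one of the two is significant at 0.05 in 28/30/39% of trials per marker.

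**Unequal variances.** The ratio for change becomes (1 + s² − 2rs)/(1 − r²). At s = 0.8:

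- r = 0.5: (1 + 0.64 − 0.80)/0.75 = 1.12, against 1.33 at s = 1
- r = 0.7: (1 + 0.64 − 1.12)/0.51 = 1.02, against 1.18 at s = 1

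At s = r the ratio is exactly 1. It is below its s = 1 value for any s between 2r − 1 and 1, and above it when s exceeds 1.

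**Repeated measures ANOVA.** With baseline and one follow-up, its arm-by-time test is the change-score test. With baseline and two follow-ups, equal correlations and equal variances, the benchmark is a baseline-adjusted analysis of the follow-up mean with 80% power. Its variance is v = (1 + r)/2 − r². The 2-df arm-by-time test then behaves as follows:

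- Same effect at both follow-ups: noncentrality 2.80² × v / (1.5(1 − r)), power 43/52/60% at r = 0.3/0.5/0.7.
- Effect at one follow-up only, with the same average effect: noncentrality 2.80² × v × 4 × (2/3)/(1 − r), power 96/99/99.7%.

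So its standing against the benchmark depends on the pattern of the effect over time.

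**The case against.** **These are exploratory outcomes of a pilot trial.** Objective 2 is only to explore, and the Dummy Tables section sends these outcomes to a separate manuscript. A rule on which p-value counts is confirmatory discipline, and the contrast with SOFA, an efficacy outcome, is no contradiction. This stands, and it makes the point minor. It does not remove it, because the better method is already in the document and needs no new data.

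**Testing both forms is partly an inference.** The table puts outcome forms in one column and a menu of methods in another, and does not explicitly assign a t-test to each form. That is fair. But the menu still names no baseline covariate and no main form.

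**The gain may be small.** At r = 0.3 the level test loses only 4 points (76% against 80%). At r = 0 there is nothing to gain: in simulation with 87 per arm, the adjusted test had 79.6% against 80.0% for level. This stands too. The change test, however, is weakest where r is low.

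**The allocation regression may already adjust for baseline.** It may, but only as an optional covariate in a secondary analysis.

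A reader might infer that a change score always loses precision, or that repeated measures ANOVA is generally inferior. Neither follows. The first fails when the SD ratio equals r, and the second reverses when the effect appears at only one of two follow-ups. The SAP excludes neither case.

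**Conclusion.** The point holds as one of efficiency and of naming a single answer per marker. Apart from one degree of freedom, a baseline-adjusted comparison is never less precise than the level test or the change test. Under equal variances and an assumed correlation of 0.3 to 0.7, the change test loses about 7 to 18 power points and the level test about 4 to 28 from 80%. Both the correlation and the equal variances are assumptions; the loss for change can be smaller, nil or larger if the SDs differ.

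A reader might go further and infer that the marker tests are invalid or that the trial's main result is at risk. The document supports neither: randomisation makes the unadjusted tests valid, and the primary endpoint is analysed separately.

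Nor is the regression on fluid balance a fault on this ground. It is an association analysis, and would mislead only under a causal reading that the SAP does not state.

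**What to change.** In the three marker rows, make the comparison between arms one ANCOVA of the follow-up value (log scale if skewed) on arm, baseline value and site. Site belongs there because "Randomisation will be stratified by study site". If a marker has several follow-up times, use a mixed model of the follow-up values with baseline as covariate and arm-by-time terms, and name the main arm contrast in advance. Keep level and change as descriptive summaries.

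The cost is SAP wording and a few degrees of freedom. Change from baseline already requires the baseline samples, and for missing values the SAP already states that "Multiple imputation will be used to deal with missing data".
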